9.1.4 Clinical Laboratory

Samples of blood and urine will be collected for clinical laboratory tests. Tests will be conducted as designated below:

9.1.4.1 Clinical Laboratory Tests Conducted

Clinical laboratory evaluations will include:

At **Screening (Visit 1)** and **Week 4 (Visit 6-EOT/ET)** - Hematology: hemoglobin, hematocrit, red blood cell (RBC) count, RBC morphology, white blood cell (WBC) count with differential, mean corpuscular volume (MCV), mean corpuscular hemoglobin (MCH), mean corpuscular hemoglobin concentration (MCHC), and absolute platelet count.

At **Screening (Visit 1)** and **Week 4 (Visit 6-EOT/ET)** - Serum Chemistry Profile: albumin, alkaline phosphatase, alanine aminotransferase (ALT; SGPT), aspartate aminotransferase (AST; SGOT), bilirubin (total and direct), blood urea nitrogen (BUN), calcium, carbon dioxide (CO2), chloride, creatinine, creatinine phosphokinase (CPK), glucose, phosphate, potassium, sodium, total protein, and uric acid.

At Screening (Visit 1) and Week 4 (Visit 6-EOT/ET) - For WOCBP a urine pregnancy test will be performed and must be negative for subjects to be enrolled.

9.1.4.2 Abnormal and Clinically Significant Results

The Investigator must categorize all abnormal hematology and chemistry laboratory values as either clinically significant (CS) or not clinically significant (NCS). Clinical significance is defined as any variation in laboratory parameters, which has medical consequences that result in an alteration in the subject's medical care. In case of CS laboratory results, the Investigator will

continue to monitor the subject with additional laboratory assessments until (1) values have reached normal range and/or baseline levels, or (2) the Investigator has judged that the abnormal values are not related to the administration of study drug or other protocol-specific procedures.

9.1.6 Ocular Scores

Ocular pain, blurred vision, photophobia and tearing will each be measured using a visual analogue scale (VAS). The VAS is a continuous 100 mm line and subjects will be asked to indicate their level of agreement to a statement (0 = no symptoms, 100 = worst possible symptoms) by placing a single vertical on the scale. The subject's completed VAS will become the source document and the response, measured in mm from the left, will be transcribed into the CRF.

The VAS will be administered at Screening, Day 4, Week 1, Week 2, Week 3 and Week 4.

9.1.7 Visual Acuity

Visual acuity will be measured with spectacle or pinhole correction at each visit. The subject will be asked to read a standardized eye chart (ETDRS). Detailed instructions on Visual Acuity Testing are provided in the Study Manual. Subjects should be encouraged to make an effort to read as many letters as possible on the chart. Distance visual acuity only will be measured. The right eye should be tested first. Visual acuity will be measured at **Screening, Day 4**, **Week 1**, **Week 2**, **Week 3** and **Week 4**.

9.1.8 **IOP Measurements**

IOP measurements will be taken using an accepted tonometry method, which includes pneumatic tonometry, Tono-Pen applanation tonometry or Goldmann applanation tomnometry – depending on the preferred method at each site. *Once a subject has enrolled in the study, the same tonometry method will be used for that subject throughout the duration of the study.* IOP will be measured at **Screening, Day 4**, **Week 1**, **Week 2**, **Week 3** and **Week 4**.

9.1.9 Slit Lamp Exam

External examination and biomicroscopy will be performed using a slit lamp. Magnification will be consistent with standard clinical practice. The clinician will examine and grade the eyelid and then examine the conjunctiva, cornea and anterior chamber of the eye with the aid of a slit lamp. Fluorescein dye will be instilled into the ocular cul-de-sac to facilitate this examination. The subject will be seated during the examination. See Appendix 1 for grading scales. ACC grade will be determined and for Grade 1+ and lower only, a numerical cell count will be obtained. Slit lamp examination will be completed at **Screening**, **Day 4**, **Week 1**, **Week 2**, **Week 3** and **Week 4**.

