9.1.11 Corneal Pachymetry

Central corneal thickness will be measured by applanation ultrasound pachymetry. For each measurement the highest and lowest of five consecutive readings will be discarded, and the average of the remaining three will be recorded. In cases where a pachymeter is used that

calculates an average central corneal thickness from five or more measurements with a single touch to the eye, this average measurement may be used for the purposes of calculating the pachymetry corrected IOP. Corneal pachymetry will be completed at **Screening**.

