# 4. INTERIM ANALYSIS AND DATA MONITORING COMMITTEE

An independent data safety monitoring board (DSMB) will be established. They will review all available safety data after approximately 25 subjects have completed the study visit 7. The assessment of safety will be determined from ophthalmologic endpoints including slit lamp examinations, ocular scores, visual acuity and IOP, vital sign measurements, physical examinations, hematology and chemistry laboratory testing, use of concomitant medications, and review of adverse events. Based on the safety data provided, the DSMB will determine if it is acceptable to continue the study or modify the study design as appropriate. Additional DSMB reviews will occur throughout the trial approximately every 6 months or as deemed necessary by the DSMB or Sponsor to ensure subject safety and well-being. Study enrollment and dosing will continue while the DSMB evaluates data. A DSMB charter will be prepared. The charter will contain the required information for the formation, activities and conduct of the DSMB.

There is no other type of interim analysis planned for this study.

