# 9.3.1. Slit Lamp External Eye Exam and Biomicroscopy

The examination of anterior uveitis is performed on both eyes (study and non-study eye) by external examination and biomicroscopy using a slit lamp. Slit lamp examination will be completed at Day 1 (Screening), Day 4, Week 1, Week 2, Week 3 and Week 4.

Changes from baseline in signs and symptoms of anterior uveitis which include Anterior Chamber Cell Grade, Anterior Chamber Flare Grade, Limbal Injection, Hypopyon, Peripheral Anterior Synechiae, Posterior Synechiae, Keratic Precipitates and Eyelid are the interest of treatment efficacy.

Descriptive summaries of the observed exam results at each scheduled visit as well as the change from baseline at each post-baseline visit will be presented for both eyes (study and non-study eye), without imputation. The numerical value of the exam result categories will be used in the summaries. The higher score representing more severe symptoms.

Number and percentage of subjects with Eyelid categories of Normal or Abnormal as well as the categorical shift from baseline at each post-baseline visit will also be summarized. The percentages will be calculated based on the number of subjects at each visit in each treatment group of the ITT analysis set. The percentages on the shift will be calculated based on the number of subjects with both baseline and post-baseline values.

In addition to the descriptive summary, the change from baseline in anterior chamber cell grade and flare grade will be analyzed using Mixed effect Model Repeat Measurement (MMRM) method. The MMRM model will include the fixed categorical effects of treatment, random effect visit, and treatment-by-visit interaction, as well as continuous fixed covariates of baseline score. An unstructured covariance structure of random effect will be used for modeling the within-subject errors. If the unstructured covariance structure matrix results in a lack of convergence, the model will be fit using covariance matrices of the following order until convergence is met:

- Heterogeneous Toeplitz
- Heterogeneous First-order autoregressive
- Toeplitz
- First-order autoregressive

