# 10.2. Ocular Safety Assessments

Specific ocular safety assessments include intraocular ocular pressure, dilated ophthalmoscopy and corneal pachymetry. Specific ocular safety assessments will be summarized on the Safety analysis set by visit for descriptive statistics only. The descriptive statistics summary will be performed separately on the study eye and on the non-study eye where it is applicable. No statistical treatment group comparison will be performed. Unless otherwise noted, unscheduled and early termination visits will be assigned to an unplanned study visit using the analysis windows described in SAP Section 3.2.9 (Table 3) in case the scheduled visit was not performed.

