# 10.2.3. Corneal Pachymetry

Central corneal thickness will be measured by applanation ultrasound pachymetry on both eyes (study and non-study eye) in micrometer (um). For each measurement, the highest and lowest of five consecutive readings will be discarded, and the average of the remaining three will be recorded. Corneal pachymetry will be completed at Day 1 (Screening) only. The average value of the three measurements will be summarized by descriptive statistics for both eyes.

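### The SAP plans no table of on-treatment conjunctival and corneal slit-lamp findings, and one of its three ocular safety assessments, pachymetry, has no post-dose value

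*Protocol*

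**What the plan says.** Protocol 9.1.9 describes the slit-lamp exam: the eyelid is examined and graded, and the clinician will "then examine the conjunctiva, cornea and anterior chamber of the eye with the aid of a slit lamp". It adds that "Fluorescein dye will be instilled into the ocular cul-de-sac to facilitate this examination". The exam is done at Screening, Day 4 and Weeks 1, 2, 3 and 4.

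The monitoring text, identical in Protocol 10.3 and SAP 4, treats the slit lamp as a source of safety data: "The assessment of safety will be determined from ophthalmologic endpoints including slit lamp examinations, ocular scores, visual acuity and IOP".

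SAP 10.2 then defines the ocular safety set: "Specific ocular safety assessments include intraocular ocular pressure, dilated ophthalmoscopy and corneal pachymetry". SAP 2.2.2.2 gives the same three items. On pachymetry, SAP 10.2.3 says "Corneal pachymetry will be completed at Day 1 (Screening) only", and Protocol 9.1.11 agrees.

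The only slit-lamp summary in the SAP is 9.3.1, under other efficacy endpoints. It covers cell grade, flare grade, limbal injection, hypopyon, both kinds of synechiae, keratic precipitates and eyelid. Its list closes with "Keratic Precipitates and Eyelid are the interest of treatment efficacy".

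**The concern.** The study drug is a topical drop given up to eight times a day, so the conjunctiva and cornea are directly exposed. Over the four treatment weeks the schedule comes to 7×8 + 7×6 + 14×4 = 154 drops per treated eye. The plan examines these tissues repeatedly with a dye, yet specifies no comparison of what is seen. Meanwhile one of the three places in the ocular safety set goes to a measurement made once, before dosing.

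What is at stake is the descriptive safety picture. A mild surface change that the investigator does not consider clinically relevant could occur more often on ADX-102 than on vehicle without appearing in any planned by-arm table.

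**Working it through.** The point rests on no power or alpha figure, so the check sets the passages side by side.

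**Step 1. What each ocular safety assessment can show.** Visits are from Protocol Table 2 and 9.1.8 to 9.1.11.

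| Item | Visits | Post-baseline visits | Looks at conjunctiva or cornea on treatment? |
|---|---|---|---|
| IOP | 6 | 5 | No |
| Dilated fundus exam | 6 | 5 | No (vitreous, retina, choroid, optic nerve) |
| Corneal pachymetry | 1 | 0 | No (Screening only) |
| Slit lamp (not in the ocular safety set) | 6 | 5 | Yes |

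So 0 of 3 named ocular safety assessments give on-treatment information on the ocular surface, and 1 of 3 has no on-treatment value at all.

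**Step 2. What the SAP tabulates from the slit lamp.** SAP 9.3.1 gives observed values and change from baseline by visit for the uveitis signs. For the eyelid it also gives normal/abnormal counts and a shift from baseline. SAP 10.2.2 plans the same counts and shift for the fundus exam. Conjunctiva and cornea, examined on the same schedule, get neither. The nearest items are limbal injection and keratic precipitates, and Protocol 5.2 names both as signs of the disease under treatment.

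**Step 3. Follow a corneal finding seen at a post-baseline visit.**

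1. Under Protocol 9.2.1, an abnormal investigational finding is reported as an adverse event only if it comes with clinical signs and symptoms, leads to stopping treatment, or is otherwise considered clinically relevant by the investigator.
2. If it qualifies, it enters the ocular adverse event summary (SAP 10.1) and the tables by system organ class, preferred term and arm (SAP 10.1.2). Fisher's exact test is added once a preferred term reaches 10% in either arm, which with 60 per arm is 0.10 × 60 = 6 subjects.
3. If it does not qualify, no SAP table by arm receives it.

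**Step 4. Can the other by-arm summaries stand in?** Ocular pain, blurred vision, photophobia and tearing on the VAS (SAP 9.3.2), BCVA (SAP 9.3.3) and limbal injection are summarized by arm and visit. Protocol 5.2 lists all of these as signs or symptoms of anterior uveitis. If the drug reduces inflammation, they may improve even while the drop irritates the surface, so the two effects cannot be separated in them. The eyelid summary is less affected by this, but it is a different tissue.

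**The case against.** The strongest reply is that surface safety is already covered. Ocular adverse events are summarized separately and by arm, with a conditional test, and also by relationship, severity and discontinuation. The Protocol 9.2.1 rule is not narrow: it admits findings with clinical signs and anything the investigator thinks relevant, and the general definition includes any unfavourable sign. That stands. A reader might infer that ocular-surface harm is never compared with vehicle, and the documents do not support this. What can escape is only the finding that meets none of the reporting conditions.

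A second reply is that protocol and SAP do not contradict each other. The protocol's own safety endpoints are adverse events, laboratory values and IOP, and the slit-lamp sentence describes what the DSMB reviews. This also stands; the point is a gap in the planned tables, not a broken commitment. Protocol 10.8 requires safety variables to be listed by subject and time point, but a listing is not a comparison by arm.

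A third reply is that the data may not exist in a form that can be tabulated. Protocol 9.1.9 says the eyelid is graded, but the conjunctiva and cornea are only examined. Appendix 1 and the CRF are not available here. This is a real limit, and it determines the cost of the fix.

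Finally, pachymetry is openly described as Screening-only and serves the IOP correction. Its place in the safety set misleads nobody, but it adds no safety information there.

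**Conclusion.** The point holds in a limited form. On-treatment conjunctival and corneal slit-lamp findings from five post-baseline exams are listed for no SAP table beyond two efficacy-classed uveitis signs, and pachymetry contributes no post-dose value to the ocular safety set. Surface safety rests on adverse event reporting and on measures confounded with the uveitis.

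A reader might also infer that placing the slit-lamp summary on the ITT set distorts it. It does not: SAP 3.1.1 requires at least one dose, so ITT and Safety have the same members and differ only if someone received the other arm's product. Nor can the number of missed findings be given. That depends on how often surface changes occur and what share investigators would not report, and the documents state neither.

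The matter is worth correcting before database lock. It affects descriptive safety reporting and leaves the primary analysis untouched. The conclusion assumes that the unseen Appendix 1 and CRF do not already lead to such a table.

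**What to change.** In SAP 2.2.2.2 and 10.2, add slit-lamp conjunctiva and cornea, together with eyelid, on the Safety set. Give normal/abnormal counts and shift from baseline by visit and arm, in the format of SAP 10.2.2. Add the number and percentage of subjects in each arm with any new or worse finding after the first dose. Move corneal pachymetry to the baseline characteristics in SAP 7.1.

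The cost is SAP wording and one or two descriptive tables, with no new visit or procedure. If the CRF does not record these findings, one normal/abnormal item for each tissue is needed. Findings caused by the uveitis will appear in both arms, so the tables should be read as a comparison with vehicle and not as rates of drug harm.

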6.1 Inclusion Criteria

All subjects entered into this trial must meet the following criteria:

- 1. Subject is willing and able to comply with the protocol requirements, has gone through the consent process and has signed an approved informed consent form.
- 2. Male or female subjects aged ≥ 18 years and ≤ 85 years.
- 3. Subjects with acute endogenous non-infectious anterior uveitis with onset of symptoms within the previous 2 weeks.* Subjects experiencing a bilateral episode of anterior uveitis may be eligible for study in both eyes. Evaluations for selective infectious etiologies, including but not limited to Syphilis, Tuberculosis (if indicated), Herpes Simplex, Herpes Zoster, CMV, Lyme Disease or other suspected infectious etiology, must be performed during the screening period or within 3 months of randomization.
- 4. Presence of 6-50 anterior chamber cells within one field of view as measured with a slit lamp microscope (Grade 1+ to Grade 3+, Appendix 1) in the study eye(s).
- 5. Subjects must have pachymetry corrected IOP <21 mmHg at baseline and nonglaucomatous cups in the opinion of the investigator with non-glaucomatous visual fields if available, and may only administer a maximum of 1 topical medication to control IOP in the study eye.
- Best corrected visual acuity (BCVA) better than or equal to 35 letters in the study eye and 65 letters in the non-study eye using ETDRS testing. Note: this criteria is also applicable for a subject with bilateral uveitis.
- 7. Females of childbearing potential must be using or willing to use a medically acceptable method (as defined by the Investigator) of birth control. Women not of childbearing potential are defined as women who are either surgically sterile or postmenopausal.

Postmenopausal women are defined as women with cessation of menstruation for 12 consecutive months prior to signing of the informed consent form.

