# 3.2.5. Missing Data and Outliers

Every attempt will be made to capture all study data. The method on how to handle the complete and/or partial missing date in the adverse events and medications will be addressed in these individual analysis sections of the SAP. Any other type of missing, unused, or spurious data will be noted in the CSR.

The primary analysis of anterior chamber cell count will be conducted on the ITT population with last observation carried forward (LOCF) for missing data. The within subject best and worst observation imputation will be used for sensitivity analysis.

The key secondary endpoints listed in Section 2.2.1.2 will be analyzed using the same data imputation approach as used for the primary endpoint.

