# 3.2.8. Study Baseline and Study Day

For purposes of analysis the baseline value is defined as the last non-missing value obtained prior to initiation of study drug, nominally the Screening Visit. Measurements that are obtained after the first dose of study drug will be considered post-baseline values. If a measurement of a variable is not made on a given subject prior to the first dose of study drug, then that subject will be considered not to have a baseline value for that parameter. Change from baseline is defined as non-missing post-baseline assessment value minus baseline assessment value.

Study day for events on or after the date of the first dose will be defined as the number of days from the date of the first dose of study drug, plus 1 day, so that the date of the first dose will be defined as Day 1. For events before the date of the first dose, study day will be calculated as the difference in days between the date of the first dose and the date of interest. Thus, the day before the date of the first dose will be defined as Day -1.

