# 9.1. Analysis of Primary Efficacy Endpoint

The primary efficacy endpoint is the time to treatment success, where such time (in days) is defined as from initiation of study drug to when a cell count of 0 is achieved and maintained (without cell count increase to > 0) to Week 4 without being rescued (or discontinued due to the requirement for rescue therapy) at any time prior to Week 4. All rescued subjects and subjects who did not achieve treatment success will be right censored. Subjects who discontinue from the study for reasons other than rescue will be real-time censored. Event and censoring definitions are described in Table 4 below.

The primary analysis to test superiority of ADX-102 over vehicle is the stratified log-rank test, stratified for the baseline ACC grade, with missing data imputed using the last observation carried forward (LOCF) approach. The Kaplan-Meier method (Kaplan and Meier 1958) will be used to estimate the time to treatment success curve. The Cox proportional hazards model with treatment group as a factor, stratified by the baseline ACC grade, will be used to estimate the hazard ratio and corresponding 95% confidence interval.

Table 4: Event and Censoring for Time to Treatment Success Analysis

Situation	Event / Censored	Date of Event / Censoring
Treatment success	Event	Date when the first cell count of 0 is achieved prior to or at Week 4 and maintained (without cell count increase to > 0) to Week 4 without being rescued any time prior to Week 4
Cell count greater than 0 at Week 4	Censored	Date of Week 4
Rescued	Censored	Date of Week 4
Early discontinuation from study for reasons other than rescue	Censored	Date of study discontinuation or Week 4, whichever is the earlier

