#### Sensitivity Analyses

The following sensitivity analyses will be conducted to evaluate the robustness of the result from the primary analysis:

- 1) *Unstratified Analysis:* An unstratified log-rank test on the ITT population with missing data imputed by the LOCF approach. The unadjusted hazard ratio and 95% CI will be estimated from Cox model.
- 2) Best Within-Subject Observation: A stratified log-rank test on the ITT population with missing data imputed by the within-subject best observation from Day 1 to Week 4 or Early Termination. The hazard ratio and 95% CI will be estimated from Cox model stratified for the baseline ACC grade.
- 3) Worst Within-Subject Observation: A stratified log-rank test on the ITT population with missing data imputed by the within-subject worst observation from Day 1 to Week 4 or Early Termination. The hazard ratio and 95% CI will be estimated from Cox model stratified for the baseline ACC grade
- 4) Subjects with Unscheduled Visits: A stratified log-rank test on the ITT population with missing data imputed by the LOCF approach. Values from scheduled and unscheduled visits will be pooled before imputation. The hazard ratio and 95% CI will be estimated from Cox model, stratified for the baseline ACC grade

Throughout this Statistical Analysis Plan, rescue will be defined as disease worsening or lack of disease improvement that, at the discretion of the investigator, requires rescue therapy. Prior to database lock, discontinued subjects will be adjudicated as to whether the discontinuation was primarily due to the requirement of rescue therapy.

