# 9.2. Analysis of Secondary Efficacy Endpoints

#### 9.2.1. Time to Cell Grade Reduction

The time to cell grade reduction is defined as the time (in days) from initiation of study drug to the date that improvement (decrease) from baseline in ACC grade of at least 1 grade was achieved without being rescued (or discontinued due to the requirement for rescue therapy) at any time prior to Week 4. All rescued subjects and subjects who did not achieve treatment success will be right censored. Subjects who discontinue from the study for reasons other than rescue will be real-time censored. Event and censoring definitions are described in Table 5 below.

Missing ACC grade will be imputed using the LOCF approach. A log-rank test stratified by the baseline ACC grade will be performed for between-group comparison. The Kaplan-Meier plot will be generated. The Cox proportional hazards model, with treatment group as a factor and

stratified by the baseline ACC grade, will be used to estimate the hazard ratio and corresponding 95% confidence interval.

Table 5: Event and Censoring for Time to Cell Grade Reduction Analysis

Situation	Event / Censored	Date of Event / Censoring
Cell grade reduction	Event	Date when the first ACC grade with at least 1 grade decrease from baseline was achieved without being rescued at any time prior to Week 4
Cell grade reduction does not meet 1 grade reduction from baseline prior to or at Week 4	Censored	Date of Week 4
Rescued	Censored	Date of Week 4
Early discontinuation from study for reasons other than rescue	Censored	Date of study discontinuation or Week 4, whichever is the earlier

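### Could an eye graded 2+ or higher, for which no cell count is taken, be scored as missing in the primary endpoint?

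*Protocol*

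**What the plan says.** Every slit lamp examination yields an anterior chamber cell (ACC) grade, but not always a number. Protocol 9.1.9: "ACC grade will be determined and for Grade 1+ and lower only, a numerical cell count will be obtained".

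SAP 9.1 defines the primary endpoint on the count. Success is dated from "when a cell count of 0 is achieved and maintained (without cell count increase to > 0) to Week 4". The success row of SAP Table 4 requires the zero to hold "to Week 4 without being rescued any time prior to Week 4", and another row censors a subject whose count is above zero at Week 4.

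The missing-data rule in SAP 3.2.5 is also on the count: "The primary analysis of anterior chamber cell count will be conducted on the ITT population with last observation carried forward (LOCF) for missing data". For the secondary endpoint in SAP 9.2.1 the wording is on grade: "Missing ACC grade will be imputed using the LOCF approach". One sensitivity analysis in SAP 9.1 has "missing data imputed by the within-subject worst observation from Day 1 to Week 4 or Early Termination".

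The link between the two measures is in Protocol 6.1, criterion 4: "Presence of 6-50 anterior chamber cells within one field of view", which that criterion equates with Grades 1+ to 3+. The grading scale itself (Protocol Appendix 1) is not in the public text.

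**The concern.** At Grade 2+ or higher the count field is blank by design, while the endpoint and its imputation rule speak only of counts. A programmer who treats every blank as missing would apply LOCF. A subject with a recorded 0 at Week 2 or 3 and an eye graded 2+ at Week 4 would then be given a Week 4 count of 0 and become an event, although the examiner saw a relapse.

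The rescue rules in SAP 2.3.4.3 do not catch all such subjects. The increase in grade is judged against Day 1, and the no-improvement criterion covers only Day 1 to Week 2. A subject who enters at 2+ or 3+, clears, and later returns to a grade no worse than at entry meets neither ACC criterion.

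At stake is whether two programmers would derive the same result for the trial's only inferential endpoint (SAP 3.2.3).

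**Working it through.** **1. The plan's power figure.** Inputs from SAP 2.3.6: hazards 0.2672 and 0.1098, 53% censoring, two-sided alpha 0.05, equal allocation. Hazard ratio = 0.1098 / 0.2672 = 0.411. Schoenfeld power = Φ(½·√events·|ln HR| − 1.96).

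- N = 90: events = 90 × 0.47 = 42.3; power 82.4% (stated 82%).
- N = 120: events = 120 × 0.47 = 56.4; power 91.6% (stated 91%).

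The figures reproduce. One misclassified subject is 1 / 56.4 = 1.8% of the events.

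**2. Where the readings differ.** A Grade 2+ visit before the first recorded 0 makes no difference, because there is no zero to carry. A positive count recorded after the relapse also removes the difference, because it breaks the run of zeros either way. The readings part only when a Grade 2+ or higher visit follows a recorded 0, the subject is not rescued, and no positive count is recorded afterwards. Seven constructed paths, scored with the ACC rescue criteria and Table 4:

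| Grades at Days 1, 4, 8, 15, 22, 29 | Blank read as missing | Blank read as > 0 |
|---|---|---|
| 2+, 1+, 1+, 0, 0, 2+ | event Day 15 | censored |
| 3+, 2+, 1+, 0, 0, 2+ | event Day 15 | censored |
| 3+, 2+, 1+, 0, 3+, 3+ | event Day 15 | censored |
| 1+, 1+, 1+, 0, 0, 2+ | event Day 15 | censored |
| 2+, 1+, 1+, 0, 2+, 0 | event Day 15 | event Day 29 |
| 1+, 1+, 1+, 0, 2+, 2+ | rescued Day 22, censored | same |
| 2+, 1+, 1+, 0, 0, 1+ | censored | same |

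Five of the seven change: four in status, one in date. The paths were chosen to test the rule, so this is not a frequency. The fourth row assumes no rescue. If rescue were given at Week 4, Table 4 is open: its success row excludes only earlier rescue, but its row for rescued subjects has no time limit.

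**3. Which reading the text supports.**

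- Criterion 4 puts Grades 1+ to 3+ at 6-50 cells. An eye graded 2+ therefore has more than 0 cells, whether or not a number is written down.
- The endpoint fails if the count rises above 0 before Week 4. A relapse to 2+ is such a rise.
- LOCF is for missing data. At these visits the eye was examined and graded; the number was never scheduled.
- The literal reading proves too much. Grade 1+ enrolment stops at 60 (Protocol 10.2), so about 120 − 60 = 60 or more subjects enter at 2+ or 3+ with no Day 1 number. Under SAP 3.2.8, "that subject will be considered not to have a baseline value for that parameter". About half the trial would then have no baseline cell count, although all were admitted on their cells.

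**4. Scale if the literal reading were used.** This rests on assumed rates that are not in the documents: 60 per arm, half entering at 2+ or higher, hazards per week, visit-based times, no dropout, unstratified log-rank, 3000 simulated trials per setting. Hazards per week imply 65.7% and 35.5% success by Week 4, or 49.4% censored on average, near the stated 53%. Suppose 5%, 10% or 20% of the non-successes entering at 2+ or higher, in both arms, were such relapses. That gives about 1.5, 3.0 or 6.0 false events, and power falls from 93.5% to 91.6%, 90.1% or 87.0%. With no true effect, upper-tail error is 2.4% with none and 2.2% at 10% in both arms. It departs from nominal if relapse differs by arm: 6.3% at 20% active against 10% vehicle, and 1.1% the other way round.

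**The case for a change.** The best case for a change is that the SAP elsewhere writes grade when it means grade (SAP 9.2.1 and 9.2.5), so a programmer might take cell count in SAP 9.1 strictly. Criterion 4 is an entry criterion, not a derivation rule. The sensitivity analyses would not always reveal the error: for grades 3+, 2+, 2+, 0, 0, 2+ the only recorded counts are zeros, so worst-observation imputation also returns 0. A written rule would cost a sentence or two and need no new data.

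Part of this stands. The rule is unwritten in the available text, and the worst-observation analysis is not a complete safeguard. The inference from vocabulary is weak, though. Protocol 5.3 stratifies on ACC score and SAP 2.3.2 on ACC grade; SAP 3.2.7 picks the study eye by cell score; SAP 3.2.5 extends the count's imputation approach to the grade-based secondary endpoints. The documents do not keep count and grade strictly apart.

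The error would also leave a trace. SAP 9.3.1 summarises ACC grade by visit without imputation, so a subject scored as a primary success would appear there at Grade 2+ at Week 4.

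**Conclusion.** This is a gap that analysts fill sensibly, and no change to the plan is needed. The plan states no wrong rule. It leaves a derivation step unwritten, and its own text points to one answer: Grade 2+ or higher is an observed count above 0, so zero has not been maintained at that visit. The harmful result needs someone to overwrite an examined and graded relapse with an earlier zero.

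Under the natural reading, event definitions, sample size and power stay as planned. The simulated losses apply only to the other reading and rest on assumed relapse rates; the documents cannot say how many subjects would be affected or how they would split between arms. The conclusion assumes that Appendix 1 agrees with criterion 4 in placing Grade 2+ above zero cells.
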